Special attention was directed to any occurrence of joint pain during the MV-CHIK study due to significant joint pathology caused by CHIKV. The subjects were asked to report any symptoms of joint pain in their subject diary and they were asked for any symptoms during each visit. Overall, 23.8% (10/42) of the subjects reported any signs of joint pain or arthralgia during the treatment period, 11.9% (5/42) of which were rated as related to the study treatment. In all 5 cases the joint pain was described as transient musculoskeletal pain, which was accompanied by flu like symptoms. Pain in the limbs associated with MV-CHIK injection was largely graded as mild (82%), was self-limiting and did not engender any withdrawals from the study. The rate of musculoskeletal pain decreased from 12% (n=5; 67% mild) at the first visit to 2% (n=1; 100% mild) at visit 5. No signs of inflammation were observed.

Severe and serious AEs occurred only for subjects treated with MV-CHIK. All serious AEs reported were non-local and unsolicited. Overall, seven severe AEs occurred (in six participants), of which five were solicited and related to vaccination including headache, local erythema, local induration, local pain and pyrexia.

The number of overall AEs and related AEs increased with the MV-CHIK dose. In addition, local reactions to MV-CHIK vaccination increased dose-dependently and were deemed related to the high inoculation volume (1mL) together with the formulation's salt buffer content.

The evaluation of safety laboratory parameters (haematology, serum chemistry, urinalysis) did not indicate any safety issues. There were no clinically relevant abnormalities observed in haematology, clinical chemistry, coagulation or urinalysis laboratory parameters.

The Clinical Study Report has been finalised in Q4/2014. The study results were published in Ramsauer et. al. Lancet Infect Dis 2015.

MV-CHIK-203:

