12.7 Missing Data

All attempts will be made to prevent missing data and generally, missing will not be imputed, and analysis will be limited to observed values. However, for missing data in AE evaluation (e.g. missing information about severity or causality) a worst-case approach will be applied.

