2.8 Handling Missing Data

Generally, missing values of immunogenicity variables will not be imputed, and the analysis will be limited to observed values. For missing data in AE evaluation concerning seriousness, severity or causality a worst case approach will be applied. In case of missing assignment to solicited or unsolicited, this AE will neither be counted in tables for solicited AEs nor in tables for unsolicited AEs but in tables for all AEs.

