2.11 Analysis Populations

2.11.1 Safety Population

The safety population is defined to include all subjects who entered into the study and received at least one IMP administration. All analysis based on the safety population will be carried out using the actual treatment received. Subjects with vaccination protocol deviations will be allocated to a treatment group after a case-by-case review in the Blind Data Review Meeting. If a subject received different doses at different visits, the minimum dose received will decide the treatment group.

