6.2.2 Derivations and Definitions

- All solicited and unsolicited Adverse Events up to day 56 (Visit 5) will be analyzed for the preliminary analysis. AE reporting and documentation is completed at Day 56. Thus all AE in the database are considered for the adverse event endpoints. In case of unexpected data change, new reported AEs or follow-up information, affected tables and/or listings may be repeated for the final analysis. Otherwise,

Adapted from:

STAT03_A Statistical Analysis Plan

Version 6.0, Effective Date 16-Feb-2018

Confidential and intellectual property of Assign DMB. No part of this document or its contents may be duplicated, referenced, published or otherwise disclosed in any form or by any means without prior written consent of Assign DMB.

Page 16 of 29

06CJDX

adverse event tables are not repeated at the final analysis. This decision may be done in a DRM prior to database closure, see [Section 2.9](#).

- Percentages for AE rates are based on N (treatment group totals).
- Medical Conditions/symptoms noted prior to first IMP administration will be reported as medical history and not as adverse events. In case of an incomplete start date where it cannot clearly be decided if the Adverse Event started before the first IMP the Adverse Event will be considered to be started before first IMP.
- An Adverse Events is considered to be related to study treatment if “Relationship to Study Treatment” is answered with “definitely”, “probably” or “possibly” or the causality is missing.
- Adverse Events where an action was taken are considered if “Action taken with Study Treatment” is answered with “Second IMP Administration Delayed” or “Second IMP not Administered”.
- Tables showing “severe” events will include events with grade 3 or 4 or missing grade.
- In tables showing subjects with AEs by maximum severity, subjects will be counted only in the highest grading category, but events will be counted in each reported grading category.
- In tables showing AEs by causality, subjects will be counted only in the strongest relationship category, but events will be counted in each category.

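### SAP 6.2.2 places an adverse event with an undecidable start date before vaccination, which can only lower on-study AE counts and departs from the protocol's worst-case rule

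*Combined protocol and SAP*

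**What the plan says.** **The start-date rule.** SAP 6.2.2 (Adverse Events, Derivations and Definitions) covers AEs whose start date is incomplete and cannot be placed relative to the first injection: "the Adverse Event will be considered to be started before first IMP". The sentence before it, in the same bullet, gives the consequence: "Medical Conditions/symptoms noted prior to first IMP administration will be reported as medical history and not as adverse events". The first bullet of that section points the other way: "Thus all AE in the database are considered for the adverse event endpoints".

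**The protocol's rule for missing AE data.** Protocol 12.7 says that "for missing data in AE evaluation (e.g. missing information about severity or causality) a worst-case approach will be applied". Severity and causality are given there as examples. SAP 2.8 narrows the list to seriousness, severity and causality, and start date is not mentioned.

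**Two neighbouring rules.**
- For an AE with no solicited/unsolicited assignment, SAP 2.8 says that "this AE will neither be counted in tables for solicited AEs nor in tables for unsolicited AEs". The sentence goes on to keep it in the tables for all AEs.
- For the Safety Population, SAP 2.11.1 says: "Subjects with vaccination protocol deviations will be allocated to a treatment group after a case-by-case review in the Blind Data Review Meeting". It then adds: "If a subject received different doses at different visits, the minimum dose received will decide the treatment group". Protocol 12.5.1 says only that safety is analysed by the treatment actually received.

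**The concern.** A default for missing data in a safety analysis should not favour the product, and this one can err only in that direction. An event wrongly placed before the injection disappears from the on-study count, and no error of the opposite kind can offset it.

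Safety is part of the primary objective (protocol 5.1), and the AE rate is the first-listed secondary endpoint (protocol 6.2.2). The trial introduces a dose of 1×10^6 TCID50, above the range of 1.5×10^4 to 5×10^5 used before (protocol 4.5). In phase I, "The number of overall AEs and related AEs increased with the MV-CHIK dose". The relation of AEs to dose is therefore something this trial should measure cleanly, and with 12 subjects per group a single reclassified subject shows.

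**Working it through.** The plan states no figure on this point and no formal sample size calculation (SAP 1.4), so there is nothing to reproduce. The check is a comparison of passages, followed by an illustration with assumed counts.

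**1. The rule against the other passages**

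| Place | Default or definition | Direction |
|---|---|---|
| SAP 6.2.2, start date undecidable | before first IMP, hence medical history | fewer AEs |
| Protocol 12.7, missing AE data | worst case | not fewer |
| SAP 6.2.2, causality missing | related | more related AEs |
| SAP 6.2.2, grade missing | counted with severe | more severe AEs |
| SAP 4.2, medication stop date undecidable | concomitant, that is, on study | more on-study records |
| Protocol 11.2, symptom reported after first vaccination | recorded as an AE | on study |

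Protocol 10.2 starts AE recording after the first vaccination. An AE record therefore already reflects the site's view that the event is on study, and the SAP rule overrides that view because part of a date is missing. If instead all AEs in the database count, the rule has no effect on the tables. The text supports both readings, so two programmers could produce different counts.

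**2. Effect of one event.** AE rates count subjects and are based on the group total (SAP 6.2.2), so the denominator stays at 12. If the subject has no other AE in that category, the rate falls by 1/12 = 8.3 percentage points. If the subject has another, it does not change.

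**3. Effect on a comparison.** Fisher exact tests are planned (SAP 2.6). With assumed counts in two groups of 12, two-sided:
- 8/12 against 2/12: p = 0.0361. Losing one event in the first group gives 7/12 against 2/12: p = 0.0894.
- 5/12 against 0/12: p = 0.0373. Losing one gives 4/12 against 0/12: p = 0.0932.

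**4. How often a date would be undecidable.** Assume that only month and year are known and that the injection day is uniform over a 30-day month. An onset k days after injection falls in the same month, and so cannot be placed, with probability (30 − k)/30, or zero for k ≥ 30. Averaging over equally likely onset days:
- days 0–6: 1 − 3/30 = 90%
- days 0–27: 1 − 13.5/30 = 55%
- days 0–56: 15.5/57 = 27%

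If 1% to 10% of AEs lacked the day (an assumed range), 0.9% to 9% of events on days 0–6, or 0.3% to 2.7% of events over days 0–56, would be placed before vaccination.

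**5. Missing AE type.** In the SAP 7.1 table list, only Tables 1.4.2 (summary) and 1.4.7 (maximum severity) cover all AEs regardless of type. The tables by symptom, or by system organ class and preferred term, are each limited to solicited or unsolicited events. An unflagged AE would be counted in those two tables and shown in Listing 1.4.3, but would appear in no table by term.

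**6. Minimum-dose rule.** Take a Group D subject who received 1×10^6 once and 1×10^5 (liquid frozen) once, with assumed counts for D against B. The rule moves the subject from D to B, so both denominators change.
- Subject with an AE: 8/12 against 2/12 (p = 0.0361) becomes 7/11 against 3/13 (p = 0.0953). The contrast narrows.
- Subject without an AE: 7/12 against 2/12 (p = 0.0894) becomes 7/11 against 2/13 (p = 0.0327). The contrast widens.

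The total number of subjects with an AE is the same either way.

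**The case against.** The strongest reply is that the start-date rule may never operate. Solicited AEs come from a diary completed daily for 7 days (protocol 11.7), the onset date is required on every AE page (protocol 10.2), and incomplete entries are queried (protocol 15.4). The safety analysis is mainly descriptive, and the primary endpoint is PRNT50 alone. All of this stands and limits the expected size. It does not justify the direction of the default or remove the conflict within SAP 6.2.2.

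Several stronger readings are tempting, but the documents do not support them.
- **Unflagged AEs are lost.** They are not: SAP 2.8 keeps them in the all-AE tables.
- **The minimum-dose rule is reassuring and applies to every mis-dosed subject.** It covers only subjects given different doses at different visits. Other vaccination deviations are allocated case by case. Step 6 shows that the contrast can move either way.
- **The rule captures all 12 Group E subjects, because placebo follows 1×10^6.** This is strained. The sentence follows one on vaccination deviations, active dose then placebo is Group E's planned treatment, and no placebo group exists. The wording is loose at most.
- **A blind meeting cannot know the dose received.** The documents do not settle this. IMP inventory records are restricted to an unblinded monitor (protocol 9.9), but the meeting works from eCRF data and monitoring reports, and wrong-dose cases are listed for its review (SAP 2.9).
- **Most undecidable events are post-vaccination, by a fixed percentage.** With uniform onset over a 31-day month, injection on the 5th leaves 26/31 = 84% of days after it, but injection on the 25th leaves 6/31 = 19%. The figure depends on the date chosen.

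**Conclusion.** The start-date rule should be changed before the preliminary analysis, which is where the AE tables are produced. It can only lower on-study AE counts, it departs from protocol 12.7 and from the SAP's other defaults, and it leaves unclear which events enter the tables. The expected effect is small and falls mainly on unsolicited AEs. The largest effect of one subject is 8.3 points on a group rate, provided that the subject has no other AE in the category. The Fisher results rest on assumed counts and pairwise comparison, and the shares of undecidable dates rest on the assumptions in step 4. The documents do not say how many dates will be incomplete.

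The missing-type and minimum-dose rules are secondary. The first is a gap in tabulation by term. The second is an incompletely defined rule whose direction of bias depends on whether the moved subject had an AE. Neither supports a claim that the SAP systematically understates harm at the high dose.

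**What to change.** **SAP 6.2.2.** Treat an AE with an incomplete start date as starting on or after first IMP unless the available date parts or the end date show otherwise. State that such AEs enter the AE tables, which also removes the conflict with the sentence on all AEs in the database.

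**SAP 2.8.** Derive a missing AE type from the data where possible, and otherwise default it to unsolicited, so that the event appears in a table by term.

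**SAP 2.11.1.** Reconcile the minimum-dose sentence with protocol 12.5.1, state that Group E's planned placebo does not trigger it, and list mixed-dose subjects separately. Replacing minimum with maximum would not be enough: that is a debatable choice, and dose alone does not identify a group, since 1×10^5 belongs to B and C and 1×10^6 to D and E.

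**Cost.** A few sentences in the SAP and no new data. The downside is that reported AE rates may be slightly less favourable, since an occasional event that truly began before vaccination will be counted as on study.

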6.3 Laboratory Parameters

Data from the early termination visit or unscheduled visits will be listed only and will not be shown in summary tables by time point. All tables will be presented by treatment group and overall. Laboratory data from scheduled visits (VS, Visit 3 and Visit 5) will be tabulated by time point. Specifications on TLFs are provided in [Section 7](#).

6.3.1 Data Points

- Hematology
 - Hemoglobin
 - Hematocrit
 - Erythrocytes
 - Leukocytes
 - Neutrophils
 - Lymphocytes
 - Monocytes
 - Basophils
 - Eosinophils
 - Neutrophils/Leukocytes
 - Lymphocytes/Leukocytes

Adapted from:

STAT03_A Statistical Analysis Plan

Version 6.0, Effective Date 16-Feb-2018

Confidential and intellectual property of Assign DMB. No part of this document or its contents may be duplicated, referenced, published or otherwise disclosed in any form or by any means without prior written consent of Assign DMB.

Page 17 of 29

06CJDX

- Monocytes/Leukocytes
- Basophiles/Leukocytes
- Eosinophils/Leukocytes
- Platelets
- Clinical Chemistry
 - Creatinine
 - Potassium
 - Sodium
 - Calcium
 - Aspartate Aminotransferase
 - Alanine Aminotransferase
 - Alkaline Phosphatase
 - Bilirubin
- Coagulation
 - Prothrombin Time
 - Activated Partial Thromboplastin Time
 - Fibrinogen
- Urinalysis
 - pH
 - Specific gravity
 - Glucose
 - Protein
 - Bilirubin
 - Urobilinogen
 - Erythrocytes
 - Leukocyte Esterase
 - Nitrite
- Urinalysis (Micro)
 - Ketones
 - Leukocytes
 - Erythrocytes
 - Casts
 - Bacteria

The following parameters will be analyzed descriptively by time point:

- Number of subjects with laboratory samples drawn for hematology, clinical chemistry, coagulation and urinalysis
- Absolute values (summary statistics for hematology, clinical chemistry and coagulation)

Adapted from:

STAT03_A Statistical Analysis Plan

Version 6.0, Effective Date 16-Feb-2018

Confidential and intellectual property of Assign DMB. No part of this document or its contents may be duplicated, referenced, published or otherwise disclosed in any form or by any means without prior written consent of Assign DMB.

Page 18 of 29

06CJDX

- Absolute change from baseline (Screening) (summary statistics for hematology, clinical chemistry and coagulation)
- Number of subjects with values above/below normal range (for hematology, clinical chemistry and coagulation)
- Urinalysis results (summary statistics for quantitative parameters, frequency statistics for qualitative parameters)

6.3.2 *Derivations and Definitions*

- No conversion of laboratory parameters will be performed. The parameters listed above will be tabulated and listed in the units reported by the study site.
- Absolute change from baseline will be calculated as difference from value of the current visit and baseline value (screening).

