7.3 Exclusion Criteria

The subject may not be enrolled in the study if any of the following applies:

1. Participation in another clinical study (including exposure to an investigational medicinal product or device) within one month before the screening visit or planned concurrent participation in another clinical study before completion of the treatment period (day 56)
2. History of immunodeficiency, known human immunodeficiency virus (HIV) infection or current hepatitis B/C infection
3. History of drug addiction including alcohol dependence within the last 2 years
4. Inability or unwillingness to avoid intake of more than around 20g alcohol per day during 48 hours after each vaccination (equals roughly 0.5 L beer or 0.25 L of wine)
5. Vaccination within 4 weeks prior to first vaccination or planning to receive any non-study vaccine until end of treatment period (day 56)
6. Prior receipt of any Chikungunya vaccine
7. History of moderate or severe arthritis or arthralgia within the past 3 months prior to Screening Visit
8. Recent infection within 1 week prior to Screening Visit (possibility of deferral)

9. Blood donations including plasma donations, 90 days prior to Screening Visit and anticipated blood, plasma, tissue, sperm or organ donation, throughout the study until end of treatment period (day 56)
10. Clinically relevant history of renal, hepatic, gastrointestinal, cardiovascular, respiratory, skin, haematological, endocrine, inflammatory, autoimmune or neurological diseases or clinically relevant abnormal laboratory values, that in the opinion of the investigator may interfere with the aim of the study
11. History of neoplastic disease (excluding non-melanoma skin cancer that was successfully treated) within the past 5 years or a history of any haematological malignancy
12. Behavioural, cognitive, or psychiatric condition that in the opinion of the investigator affects the ability of the participant to understand and cooperate with the study protocol
13. History of severe adverse reactions to vaccine administration, including anaphylaxis and related symptoms, such as urticaria, respiratory difficulty, angioedema and abdominal pain to vaccines, or history of allergic reaction likely to be exacerbated by any component of the vaccine
14. History of anaphylaxis to drugs or other allergic reactions, which the investigator considers compromising the safety of the volunteer

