8.7 Early Termination Visit (ET)

Subjects who are withdrawn or wish to discontinue the study prematurely for any reason shall be asked to attend an early termination visit.

If the early termination occurs within the treatment period (at or before Visit 5), subjects shall perform all procedures as defined for Visit 5. If the early termination occurs within the follow up period (after Visit 5), subjects shall perform all procedures defined for Visit 7.

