8.11.1 Samples for Safety Laboratory Parameters

Safety laboratory parameters will be analysed by local laboratories according to applicable laboratory SOP

The following parameters will be measured to evaluate inclusion and exclusion criteria only once at screening visit (SV).

- Virology: Hepatitis B surface-Ag, anti-Hepatitis B core-Ab, anti-Hepatitis C-Ab, HIV Ab. HIV tests that were performed up to 30 days before screening and where results are available are acceptable and do not require a new test.

The following laboratory parameters will be assessed for subject's safety at screening, Visit 3, Visit 5 and additionally at Early Termination (if applicable) as depicted in Table 2.

- Haematology: haemoglobin, haematocrit, erythrocyte count, differential and total white blood count, platelets
- Chemistry: creatinine, potassium, sodium, calcium, AST, ALT, alkaline phosphatase, bilirubin
- Coagulation parameter: prothrombin time (PT), activated partial thromboplastin time (aPTT), fibrinogen
- Urinalysis: a standard urine test dipstick for determining pH-value, glucose, protein, bilirubin, urobilinogen, blood, leucocytes esterase, nitrite, ketone and specific gravity will be used. In case of abnormal findings, a microscopy will be done for confirmation.
- Laboratory values deviating from the normal ranges defined by the local laboratory will be evaluated by the investigator. Clinically relevant deviations have to be reported as adverse events and graded according to the FDA Guidance for Industry (Toxicity Grading Scale for Healthy Adult and Adolescent Volunteers Enrolled in Preventive Vaccine Clinical Trials, Sept. 2007)

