1.4.18	n/a	Subjects with related severe unsolicited Adverse Events by SOC and PT (Safety Population)	
1.4.19	n/a	Subjects with related serious unsolicited Adverse Events by SOC and PT (Safety Population)	
1.4.20	n/a	Subjects with related medically attended unsolicited Adverse Events by SOC and PT (Safety Population)	
1.4.21	n/a	Subjects with unsolicited Adverse Events leading to second Vaccination not administered (Safety Population)	
1.4.22	n/a	Subjects with unsolicited Adverse Events caused study discontinuation (Safety Population)	
1.4.23	n/a	Subjects with at least one unsolicited Adverse Event by Maximum Severity (Safety Population)	
1.4.24	n/a	Subjects with at least one medically attended unsolicited Adverse Event by Maximum Severity (Safety Population)	
1.4.25	n/a	Subjects with at least one unsolicited Adverse Event by Causality (Safety Population)	
1.4.26	n/a	Subjects with at least one medically attended unsolicited Adverse Event by Causality (Safety Population)	
1.4.27	n/a	Subjects with at least one serious unsolicited Adverse Event by Causality (Safety Population)	
Laboratory Parameters			
1.4.28	n/a	Absolute Values for Hematology Parameters by Parameter and Visit (Safety Population)	
1.4.29	n/a	Absolute Values for Clinical	

Adapted from:

Page 24 of 29

STAT03_A Statistical Analysis Plan

Version 6.0, Effective Date 16-Feb-2018

Confidential and intellectual property of Assign DMB. No part of this document or its contents may be duplicated, referenced, published or otherwise disclosed in any form or by any means without prior written consent of Assign DMB.

06CJDX

		Chemistry Parameters by Parameter and Visit (Safety Population)	
1.4.30	n/a	Absolute Values for Coagulation Parameters by Parameter and Visit (Safety Population)	
1.4.31	n/a	Absolute Changes from Baseline for Hematology Parameters by Parameter and Visit (Safety Population)	
1.4.32	n/a	Absolute Changes from Baseline for Clinical Chemistry Parameters by Parameter and Visit (Safety Population)	
1.4.33	n/a	Absolute Changes from Baseline for Coagulation Parameters by Parameter and Visit (Safety Population)	
1.4.34	n/a	Subjects with Hematology Parameters Outside Normal Range by Parameter and Visit (Safety Population)	
1.4.35	n/a	Subjects with Clinical Chemistry Parameters Outside Normal Range by Parameter and Visit (Safety Population)	
1.4.36	n/a	Subjects with Coagulation Parameters Outside Normal Range by Parameter and Visit (Safety Population)	

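### The planned laboratory tables cannot show how many subjects per arm became newly abnormal after vaccination, and they leave out early-termination and unscheduled samples

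*Combined protocol and SAP*

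**What the plan says.** SAP 6.3.1 asks for the "Number of subjects with values above/below normal range (for hematology, clinical chemistry and coagulation") as a descriptive summary by time point. SAP 6.3 fixes the time points: "Laboratory data from scheduled visits (VS, Visit 3 and Visit 5) will be tabulated by time point". The same section states: "Data from the early termination visit or unscheduled visits will be listed only and will not be shown in summary tables by time point".

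The table list in SAP 7.1 follows this. Table 1.4.34 is "Subjects with Hematology Parameters Outside Normal Range by Parameter and Visit (Safety Population"), and Tables 1.4.35 and 1.4.36 repeat it for chemistry and coagulation. Screening serves as baseline only in the change-from-baseline summaries (Tables 1.4.31 to 1.4.33, and 1.4.38 for two urine measures). SAP 6.3.2 defines that difference: "Absolute change from baseline will be calculated as difference from value of the current visit and baseline value (screening"). No shift table, count of newly abnormal subjects or worst-value summary is listed.

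Three protocol sections bear on this:
- **Entry.** Exclusion criterion 10 (section 7.3) bars only "clinically relevant abnormal laboratory values, that in the opinion of the investigator may interfere with the aim of the study". A subject can enter with an out-of-range value that does not meet that description.
- **Extra samples.** Under section 8.7, someone who leaves at or before Visit 5 is sampled: "subjects shall perform all procedures as defined for Visit 5". Those procedures include safety laboratory tests. Section 8.8 leaves the content of unscheduled visits to the investigator and has everything done there entered in the eCRF.
- **Adverse events.** Section 8.11.1 says: "Clinically relevant deviations have to be reported as adverse events and graded according to the FDA Guidance for Industry".

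**The concern.** A reader of a vaccine safety table wants to know how many subjects in each arm moved out of range after vaccination. A count at each visit that ignores Screening status does not answer this. It mixes abnormalities already present with new ones, and the Screening column supplies only a group total to set against it.

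The second gap concerns who is missing. Scheduled safety samples after vaccination exist only at Visit 3 and Visit 5. For a subject withdrawn before Visit 3, the early-termination sample may be the only post-vaccination laboratory value. For one withdrawn between Visits 3 and 5, it may be the only value after the second injection. The stated rule drops exactly these samples from the laboratory tables.

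Safety laboratory parameters are a named secondary endpoint (protocol 6.2.2, SAP 1.3.2). The SAP already handles both issues for adverse events: section 6.2.2 assigns conditions noted before the first administration to medical history, and counts each subject at the highest grade. The laboratory tables apply neither principle.

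**Working it through.** The plan states no laboratory rate, and no formal sample size calculation was made, so there is no figure of its own to reproduce. The main check is textual. The arithmetic below only illustrates size.

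**Inputs from the documents.** There are 60 subjects in 5 equal arms, so 12 per arm. SAP 6.3.1 lists 15 haematology, 8 chemistry and 3 coagulation parameters: 15 + 8 + 3 = 26.

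**Assumed inputs.** A single value falls outside the normal range with probability p = 5% (range 2.5% to 10%). For the between-visit calculations, values are normal with limits at ±1.96 SD, and the correlation r between visits is 0.5 to 0.8.

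**1. What group totals can reveal.** Suppose *a* of 12 subjects are out of range at Screening and *b* at a later visit, with all 12 measured at both. The number newly out of range lies between max(0, b − a) and min(b, 12 − a).

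| Screening *a* | Later *b* | Newly out of range |
|---|---|---|
| 3 | 3 | 0 to 3 |
| 2 | 4 | 2 to 4 |
| 4 | 2 | 0 to 2 |

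The counts are illustrative. The width of the interval is what the planned tables leave undetermined.

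**2. Chance flags.** Per parameter, arm and visit, 12 × 0.05 = 0.6 subject is expected out of range (0.3 to 1.2 over the range of p). The probability of at least one among 12 is 1 − 0.95^12 = 46% (26% to 72%). Summed over parameters, 26 × 12 × 0.05 = 15.6 flags per arm and visit, and 26 × 60 × 0.05 = 78 over all arms.

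**3. Share already present.** P(out on the same side at Screening | out at the later visit) = P(both below −1.96) / 0.025. New flags per arm and visit are then 15.6 × (1 − share).

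| r | Share already present | New flags per arm and visit |
|---|---|---|
| 0.5 | 18% | 12.7 |
| 0.6 | 25% | 11.7 |
| 0.7 | 33% | 10.4 |
| 0.8 | 44% | 8.7 |

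**4. What a worst-value count would still contain.** I simulated three visits with equal correlation between each pair, and counted a flag if a subject was newly out of range at Visit 3 or Visit 5. Summed over the 26 parameters, this gives about 23 chance flags per arm at r = 0.5 and 15 at r = 0.8. That is as many as, or more than, a single planned by-visit column. The added table says which subjects changed; it does not remove chance findings.

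**5. Early-termination and unscheduled samples.** The documents give no expected number of early leavers or unscheduled samples, so this part cannot be sized.

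**The case against.** The strongest reply is that the information survives elsewhere. Listings 1.4.33 to 1.4.35 show each out-of-range haematology, chemistry and coagulation value with subject, treatment, visit, clinical significance, likely cause and change from baseline. Under SAP 6.3 the early-termination and unscheduled values are listed as well. With 60 subjects, a patient reader can work out by hand most of what is new. This stands, and it limits the point to summary presentation.

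A reader might infer that values from early leavers or unscheduled visits never reach any table. The documents do not support that. Protocol 8.11.1 makes clinically relevant deviations graded adverse events, and SAP 6.2.2 takes all adverse events in the database, so these deviations reach the adverse event tables whichever type of visit produced them. Protocol 8.9.1 also keeps subjects who are only stopped from further vaccination in scheduled follow-up, so their Visit 3 and Visit 5 values remain. What remains of the concern is that the adverse event route depends on the investigator's judgement of relevance and is not an objective count.

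A reader might also infer that chance flags swamp the tables. The tables are by parameter, where the expectation is 0.6 subject per arm and visit. The total of 15.6 arises only by adding 26 parameters, and it rests on an assumed rate.

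Finally, the analysis is descriptive, no stopping rule rests on it, and randomisation balances pre-existing abnormalities between arms on average. All true, and the reason this is a minor point. Average balance does not help much in a particular table with 12 per arm.

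**Conclusion.** The point holds in a limited form. Tables 1.4.34 to 1.4.36 cannot give the number of subjects newly out of range per arm, and the laboratory summary tables omit early-termination and unscheduled samples. Both follow directly from the SAP text and need no assumption.

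The size is modest. Under the assumed 5% rate and correlations of 0.5 to 0.8, roughly one in five to just over two in five later flags would be carried over from Screening. The effect of the omitted samples is unknown. No data are lost, the primary endpoint is untouched, and clinically relevant deviations are covered as adverse events. This is an inexpensive improvement to a named secondary safety endpoint, not a flaw that puts the trial's conclusions at risk.

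**What to change.** Keep the by-visit tables. For haematology, chemistry and coagulation, add a shift table by arm: low, normal or high at Screening against the worst post-vaccination category up to day 56, with early-termination and unscheduled samples included. Report the number newly out of range (normal, or on the other side, at Screening). Use as denominator the subjects with a Screening value and at least one post-vaccination value. State in advance how a subject with both a low and a high value after vaccination is placed.

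The cost is some extra programming on data already collected, plus a footnote that unscheduled samples come more often from symptomatic subjects. Grading every value on the FDA scale is optional: the documents do not contain the laboratory cut-offs, and SAP 6.3.2 plans no unit conversion, so it would add work beyond the table itself.
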